4.3 Data Collection Indicators

4.3.1 Demographic indicators: Gender, age, ethnicity.

4.3.2 Disease-related indicators: Primary disease and its treatment, disease course, previous HSCT history, chronic disease history (diabetes, hypertension, dyslipidemia, cardiovascular/cerebrovascular diseases, fatty liver, etc.), medication use.

4.3.3 Nutrition-related indicators

4.3.3.1 Body weight and body composition analysis (by bioelectrical impedance, TANITA TBF-410).

4.3.3.2 Handgrip strength.

4.3.3.3 PG-SGA score.

4.3.3.4 Dietary intake: Weighed food record method; each patient will be provided with a food scale to weigh and photograph food.

4.3.3.5 Laboratory tests: Complete blood count, liver/kidney function, blood glucose, lipids, electrolytes, serum calcium/phosphorus/magnesium.

4.3.4 Intestinal function assessment

4.3.4.1 Gastrointestinal symptoms: Frequency of nausea, vomiting, diarrhea.

4.3.4.2 Stool consistency and volume. Collect 2ml of stool, vacuum dry and freeze; measure gut microbiota diversity using 16s rRNA sequencing.

4.3.4.3 Gut microbiota metabolites in blood and urine.

4.3.5 Clinical outcome-related indicators

4.3.5.1 Length of stay in the transplant unit and total hospital stay (days).

4.3.5.2 Incidence of infections during hospitalization.

Statistical plan

Paired t-tests will be used for within-group changes in continuous data at baseline, and independent samples t-tests for between-group comparisons. Chi-square tests will be used for categorical data. Multiple linear regression will be used to analyze factors related to weight, handgrip strength, transplant unit stay, and hospital stay. Multiple logistic regression analysis will be used to analyze factors related to hospital-acquired infections. Confounding factors included in the models will be based on univariate regression analysis results and clinical experience.

1. Patient daily energy requirements will be calculated using the Schofield equation for Resting Energy Expenditure (REE). For age 18-30: Male: $63 \times \text{Weight}(\text{kg}) + 2896$; Female: $62 \times \text{Weight}(\text{kg}) + 2036$. For age 30-60: Male: $48 \times \text{Weight}(\text{kg}) + 3653$; Female: $34 \times \text{Weight}(\text{kg}) + 3538$. Stress factors will be considered based on the formula result.
2. According to the Chinese Medical Association Parenteral and Enteral Nutrition Branch guidelines for adult Oral Nutritional Supplementation, the recommended single-day ONS dose for adults is 300-900 kcal, hence the dose is set at 500 kcal/day. Supplementation starts from the pre-transplant preparation period and continues until discharge from the transplant unit.
3. Dietary intake will be assessed using 24-hour dietary recall combined with the weighed food record method.
4. Microbiota metabolites will be analyzed using metabolomics.

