4.2 Sample Size Calculation

The primary objective of this trial is to compare the change in body weight before and after treatment between the control group and the FSMP supplementation group. The sample ratio is 1:1, with a two-sided significance level (α) of 0.05 and power ($1-\beta$) of 85%. Based on our previous work, the conventional treatment group is expected to have a weight loss of -1.2kg, while the conventional treatment + FSMP group is expected to have a weight loss of -0.5kg. Approximately 37 subjects are needed per group, requiring 74 subjects in total for both groups. Considering compliance and loss to follow-up, the sample size for each group will be increased by 20%, requiring a total of 100 subjects. All enrolled patients will be stratified by disease course (newly diagnosed vs. relapsed) and HSCT type (autologous vs. allogeneic) and then randomly divided into two groups (n=50 each):

① **Control Group:** According to the hematology department's routine, provide a low-residue semi-liquid diet, supplemented with ordinary homogenized meal replacement powder (500 kcal/day, orally in two divided doses).

② **Oral FSMP Supplementation Group:** According to the hematology department's routine, provide a low-residue semi-liquid diet, additionally supplemented with Ensure (500 kcal/day, orally in two divided doses).

Oral FSMP supplementation will start from the beginning of the pre-transplant preparation phase and continue until discharge from the transplant unit.

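### Regression covariates are chosen by univariate results and judgement, and no planned analysis is committed to arm, baseline value or the stratification factors

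*Combined protocol and SAP*

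**What the plan says.** All analysis rules are in the short Statistical plan that follows section 4.3.5.

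- Treatment comparisons: "independent samples t-tests for between-group comparisons" for continuous data, and "Chi-square tests will be used for categorical data". Neither is described as stratified or adjusted.
- Regressions: "Multiple linear regression will be used to analyze factors related to weight, handgrip strength, transplant unit stay, and hospital stay", and "Multiple logistic regression analysis will be used to analyze factors related to hospital-acquired infections".
- Covariates for these models: "Confounding factors included in the models will be based on univariate regression analysis results and clinical experience".
- Randomisation, section 4.2: "All enrolled patients will be stratified by disease course (newly diagnosed vs. relapsed) and HSCT type (autologous vs. allogeneic") before allocation to two groups of 50. The Statistical plan mentions neither factor.

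Section 4.3 lists what is collected: demographics; disease items, including "chronic disease history (diabetes, hypertension, dyslipidemia, cardiovascular/cerebrovascular diseases, fatty liver, etc.), medication use"; laboratory panels; dietary intake; gastrointestinal symptoms. It does not say which of these may enter a model. Factors that influence nutritional status are a declared aim, both in Research Significance (section I) and in the objectives that close section II.

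**The concern.** Three things are left to the data or to later judgement.

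1. **Strata.** Stratified randomisation balances the arms on disease course and HSCT type. An analysis that ignores strata related to outcome still counts the between-stratum variation as noise, so its standard error is too large and the benefit of stratifying is lost.
2. **Adjusted arm estimates.** The covariate set will depend on which univariate results turn out strong. Items such as intake and gastrointestinal symptoms during supplementation are measured after randomisation and may be changed by the product. Adjusting for them removes part of the effect being estimated. Confounding is also the wrong basis for selection here, because randomisation leaves no systematic confounding of arm.
3. **Reported factors.** With no list and no exploratory label, a significant factor cannot be judged against the number of candidates tried.

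Weight and handgrip strength are primary outcomes, so readers will give these models weight.

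**Working it through.** **The plan's own figure.** The plan gives no figure for the regressions. Its sample size helps to set a scale for the effect. Section 4.2 gives a difference of 1.2 − 0.5 = 0.7 kg, 85% power, and a test "with a two-sided significance level (α) of 0.05", but no SD. With SD = 1.0 kg, n = 2 × (1.960 + 1.036)² × 1.0² / 0.7² = 36.6, that is 37 per group as stated. SD 0.9 gives 30 and SD 1.1 gives 45. The stated figure therefore implies an SD of about 1.0 kg and an effect of about 0.7 SD.

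**Unadjusted test with strata ignored.** Assumptions, none from the documents: one binary stratum split equally, a stratum effect of 0.8 SD, within-stratum SD 1, 50 per arm, arms balanced within strata.

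- True standard error of the difference: √(4/100) = 0.200.
- Variance seen by the t-test: 1 + 0.8² × 0.25 = 1.16, so SD 1.077.
- Critical difference, unadjusted: 1.984 × 1.077 × 0.200 = 0.427. Stratum-adjusted: 1.985 × 0.200 = 0.397.
- Null rejection, unadjusted: 2 × P(Z > 0.427/0.200) = 3.3%. The adjusted test holds about 5%.
- Power at 0.5 SD, unadjusted: P(Z > (0.427 − 0.5)/0.200) = 64%. Adjusted: P(Z > (0.397 − 0.5)/0.200) = 70%.
- Power at 0.7 SD, same formulas: 91% against 94%.

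The documents do not give the stratum split. With 10% of patients in one stratum the variance term is 0.64 × 0.09 = 0.058. Null rejection is then about 4.1% and power at 0.5 SD about 68%, so the loss shrinks.

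**Arm kept in the model, baseline covariates screened.** Simulation, 3,000 trials per setting, total N of 76 and 100, 10 or 20 candidates of which two are real (0.3 SD each), stratum effect 0.8 SD, screen at p<0.05 or p<0.10:

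| Analysis | Mean estimate, truth 0.70 | Null rejection |
|---|---|---|
| Unadjusted t-test | 0.70 | 2.8-3.4% |
| Arm + screened covariates, stratum omitted | 0.65-0.68 | 2.5-3.4% |
| Arm + stratum + screened covariates | 0.65-0.68 | 4.3-5.7% |
| Arm + stratum + real covariates, pre-specified | 0.70 | 4.6-5.4% |

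Power at 0.70 for the t-test against the pre-specified model was about 87% against 96% (N=76) and 95% against 99% (N=100). That gap includes the gain from the two real covariates as well as the stratum.

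**Post-randomisation covariate.** Suppose the product shifts a mediator by 0.5 to 1.0 SD and the mediator affects the outcome with slope 0.3 to 0.5 (assumptions). With a true total effect of 0.70, adjustment leaves 0.70 − 0.5 × 0.3 = 0.55 down to 0.70 − 1.0 × 0.5 = 0.20. In simulation a univariate screen admitted such a variable in 95-100% of trials.

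**False factors.** The chance of at least one p<0.05 among k independent unrelated candidates is 1 − 0.95^k.

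| k (assumed) | Formula, no screen | Simulated, screen then multivariable model, all noise |
|---|---|---|
| 10 | 40% | 39-40% |
| 15 | 54% | 50-53% |
| 20 | 64% | 60-61% |

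With two real candidates among the 10 or 20, the simulated rates are 17-28% and 35-50%. All rates are per outcome, and five outcomes are modelled.

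**The case against.** The strongest reply is that these regressions are not the treatment analysis. The plan gives that to the t-test and chi-square test, and the regressions serve the separate aim of finding influencing factors. This stands. The t-test estimate is unbiased and is reported whatever a regression retains.

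A reader might nevertheless infer that the selection rule inflates the treatment effect, or that arm itself can be screened out. The documents do not support this. The rule concerns confounders, and arm is the exposure; nothing says that arm is screened. With arm in the model the estimate is slightly small, not large, and null rejection is at or below nominal when the stratum is omitted. Inflation needs arm to be screened and reported only when kept. Even then it depends on a small effect: in the simulations a true 0.35 SD was reported as 0.43-0.52, but a true 0.70 SD, about what the sample size implies, as 0.67-0.72.

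Two further replies also stand. The false-factor rates follow the no-screen formula closely, so they come from the number of candidates, and deleting the screen would not remove them. Section 4.3 is a data-collection list, not a candidate list.

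Clinical experience could bring in the strata. That is possible, but it is not a commitment, and it does not reach the t-test or chi-square test.

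**Conclusion.** The point holds as one about covariate choice and unused strata. The plan has a data-dependent covariate rule and commits no analysis to the factors used to stratify randomisation.

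- **Main treatment tests:** valid but conservative if the strata are prognostic. Under the assumed 0.8 SD effect and equal split, null rejection is about 3% instead of 5%. Power is about 64% instead of 70% at 0.5 SD, and 91% instead of 94% at 0.7 SD. The loss is smaller if the split is uneven and absent if the strata do not matter.
- **Adjusted arm estimates:** dependent on data-driven selection, and open to distortion if post-randomisation variables enter. The plan does not say that they will; it does not exclude them.
- **Reported factors:** often false, in about 40-60% of analyses per outcome with 10 to 20 unrelated candidates, and less often if some are real.

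The calculations used one binary stratum, independent covariates and linear models. The logistic infection model was not simulated, so no figure is offered for it.

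**What to change.** Replace the covariate-selection sentence in the Statistical plan:

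- **Linear models that estimate the arm effect** (weight, handgrip strength, both lengths of stay): pre-specify randomised arm, baseline value where one exists, disease course and HSCT type. Use no univariate screen and no post-randomisation covariates.
- **Logistic model for infection:** include arm and, if the number of events allows, the two strata. State the event rule in advance.
- **Wider search for influencing factors:** keep it, label it exploratory, list the candidates, and report all of them with the number tried. The label does not lower the false-factor rate, but it lets readers judge it.

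The cost is wording only, with no change to recruitment, data collection or treatment. The downside is that fewer prognostic factors are explored in the main models.
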